Patients and study coordinators will enter baseline demographic, gout history, patient reported outcomes (PROs) directly into electronic case report forms into a 21CFR and HIPAA compliant REDCap (Nashville, Tennessee) system. We will host REDCap on one of several access-controlled, encrypted servers housed at UAB. Subsequent PROs and other outcome data will be captured by phone in the same REDCap database by the study teams. Baseline laboratory data and medication data will be obtained from our respective EMRs and will be reviewed during the phone calls and by the research assistant during the ED visit.

B.8 Study Outcomes

Study outcomes (**Table 2**) will be collected from patients at 6 weeks and 3 months following the initial ED visit with questionnaires deployed using computer assisted telephone interviews (CATI) programmed in REDCap. Validated items about gout flares and gout medications have been used in the past by our team.⁸⁴

B.8.1 Primary outcomes Aim 1 and 2.

The primary outcome of aim 1 will be the ability of the alert to successfully identify gout patients. For aim 2, it will be the proportion of patients that have a follow-up visit addressing gout in the 3-month period after the ED visit. Many gout patients are not adherent with their follow-up visits due to a lack of awareness of the consequences of untreated

gout, poor care access, and/or inadequate assistance to obtain a follow up visit. Even rapidly-scheduled outpatient visits (next business day) following an ED encounter are only attended by 73% of those seen in a recent study and rates of post-ED follow-up for many chronic disease are closer to 50%.^{91, 92} Moreover, most patients, ~80%, leave the ED with knowledge deficits that impact adherence and outcomes.^{93, 94} Having a usual source of primary care and establishing continuity of care after an ED visit is critical to optimal disease outcomes in all chronic diseases including gout.³⁰⁻³² This data will be captured both by self-report on surveys (this will be the primary study outcome) and by review of EMR data within our respective healthcare systems. While self-report will be impacted by recall and possible social desirability bias, this should be non-differential (bias towards the null).⁹⁵ EMR data will be more accurate for some outcomes but will miss any gout care delivered outside our urban Southeastern medical centers and their satellite facilities.

B.8.1.1 Secondary outcomes - Aim 2

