Secondary Outcomes / Covariates				
Social Determinants of Health				
Environmental and social factors	X			
Gout medical care				
Number of gout flares (Gaffo criteria) ^{79, 84}	X	X	X	
Rates of urate lowering therapy (ULT)**	X	X	X	
ULT adherence		X	X	
Opioid prescriptions*	X	X	X	
Weight reduction		X	X	
Healthcare resource utilization (visit number)				
ED visits (indicative of recidivism)*		X	X	
Hospitalizations*		X	X	
Health-related quality of life				
European Quality of Life (EQ-5D) ⁸⁶⁻⁸⁸	X	X	X	
Shared decision making: CollaboRATE scale ⁹⁰		X	X	

* gout follow-up within 3-months of ED visit. ** Assessed through chart or system review

randomized 2:1 stratified by race/ethnicity, to the intervention (storytelling +/- patient navigation) or control arm (usual care). All intervention arm patients in the UAB ED also will be assigned lay navigators to provide personalized support for care transitions and access to post-gout flare medical services needed for preventing recurrent flares.

The following procedures will be completed during the index ED visit:

- Review inclusion/exclusion criteria for registry participation
- Informed Consent
- Review of current/past gout status and medication chart review
- Pain Assessment
- Laboratory
 - Serum uric acid (from chart review)
 - Sample banking
- Survey assessments
 - HRQL
 - SDOH

Laboratory draw will be done in conjunction with ED care blood draw when possible. At the conclusion of visit, participants randomized to navigator arm will be provided navigators picture, contact information, and informed that they will receive a call w/in 72 hours.

B.9.1.2 *Patient Navigator Contact*

72 hours post ED visit

During this initial phone conversation the navigators will: 1) conduct a baseline assessment to identify barriers to attending an outpatient visit for gout care (e.g. transportation) and to adhering to gout treatment recommendations (medications, diet, exercise) and, 2) determine the level of support and assistance (e.g. transportation support) needed by patient. The patient navigator will help facilitate the follow-up visit with a primary care/gout specialist, identify any barriers (e.g. lack of trust in primary care physician or/and healthcare system), and provide institutional/community resources that can be mobilized for the patient.

4 weeks post ED visit and 24-48 hours prior to appointment (anticipated)

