The navigator will conduct two additional follow-up calls at approximately one month (4 weeks) and in the week (anticipated) prior to their visit to confirm the appointment time, the level of support needed (as needs may have changed), and encourage him/her to keep their appointment. In the unlikely event that the appointment with the PCP/gout specialist is sooner than one month, this one-month pre-appointment call will be eliminated and the navigator will have only two calls with the patient.

B.9.1.3 *6 Week Follow-up Assessment*

At 6 weeks following ED visit, participants will be contacted by the Coordinating Center (CC) to to assess project outcomes via a telephone survey. The following information will be collected, and data collected via the surveys and EMR. Following completion of the follow-up surveys the study coordinator will inform and debrief the patient that they participated in a study evaluating methods to improve continuity of gout care. The debrief will be conducted after the 1st survey. If RA the coordinator is unable to reach participant on the phone, the survey questions used to collect the primary outcomes will be sent via email or text messaging using Mosio, which is an HIPAA-compliant application.

- Survey assessments
 - Patient satisfaction
 - HRQL
 - PROs
- Updated medical history and review of concomitant medications
- Assessment of Adverse Events (AEs) (as meeting NIH definition of Phase III study AEs will be collected)

B.9.1.4 *3 Month Follow-up Assessment*

At 3 months (anticipated) post ED visit participants will be contacted to complete a second follow-up survey and end of study (EOS) via telephone to assess secondary outcomes (e.g. adherence to orders, medication RX, and labs (if ordered)).

- Survey assessments
 - Patient satisfaction
 - HRQL
 - PROs
- Updated medical history and review of concomitant medications
- Assessment of Adverse Events (AEs) (as meeting NIH definition of Phase III study AEs will be collected)

B.9.1.5 **Table 1 Visit Schedule**

Visit description / Study procedures	Screening and Enrollment (ED)	V1 (phone)	V2 (phone)	V3	V4 EOS
	Day 0	72 Hours	4 WK	6 WK [°]	3 MO
Review of Inclusion/exclusion criteria following alert notification	X				
Informed consent for INSIGHT Registry	X				
Medical history	X				
Laboratory					
SUA	X				
Sample banking	X				
Randomization	X				
Patient Navigator Contact#		X	X ^{\$}	X ^{\$}	
Updated medical history and concomitant medications		X	X	X	X

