Outcome ascertainment	X			X	X
Study debriefing				X	
Assess AEs			X	X	X

[°]Primary outcome assessment will occur at any point upto 6 weeks post ED visit dependent on routine care visit; # For individuals randomized to navigation arm; ^{\$}Navigator will contact participant in the week prior to scheduled follow-up visit

B.9.1.6 **Blinding and Unblinding**

Participants will blinded to study assignment at enrollment, and following primary outcome ascertainment will be debriefed regarding the study and its purpose/goals.

B.10 Statistical Analysis Plan

B.10.1 Primary Outcome Analysis - Aim 1.

All analyses will adhere to the principles of rigor, reproducibility and transparency.^{109, 110} To determine the effectiveness of our alert system, we will examine the diagnostic properties (sensitivity/specificity) of the EMR alerts against a gold standard of NLP/ML detection (section C.4.2)

B.10.2 Primary Outcome Analysis- Aim 2.

Descriptive statistics, including measures of central tendency (means for continuous, proportions for categorical) and dispersion (variance, interquartile range) will summarize the distribution of baseline characteristics of randomized patients seen in both EDs. Descriptive statistics will be summarized by treatment arm as well as enrollment site. These statistics will inform the successfulness of randomization in creating comparable groups and ascertain our success in recruiting the populations we seek to target (particularly under-represented minorities). We also will compare the descriptive characteristics between those participants who do and don't respond to follow-up surveys to detect and report any evidence of a selective non-response bias. The primary analysis approach for testing treatment effect will be a multivariable logistic regression

model. We have chosen multivariable logistic regression over Cochran-Mantel-Haenszel approaches to allow for effect estimation of multiple covariates (race, gender, age) upon the primary outcome and to allow tests of interactions. Logistic regression models, including interaction terms, will be developed for 6 week outcomes and 3 month outcomes. We will examine the significance of the effects of the intervention as the outcome of persons receiving at least one outpatient gout follow-up visit at 3 months. We will analyze rates on an intent-to-treat basis for the primary analysis. We will conduct all analyses using SAS 9.4 (Cary, NC)

[figure not shown]

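### The Aim 2 primary time point is stated as both 3 months and 6 weeks, and if 3 months is meant, the debrief comes about 7 weeks before the primary window closes

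*Combined protocol and SAP*

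**What the plan says.** **Text that sets 3 months.** B.8.1 defines the Aim 2 primary outcome: "it will be the proportion of patients that have a follow-up visit addressing gout in the 3-month period after the ED visit". The footnote attached to the primary-outcome row of Table 2 reads "gout follow-up within 3-months of ED visit". B.10.2 tests the intervention on having at least one gout follow-up visit at 3 months. B.11 gives both the expected non-response for the primary outcome (30%) and the control proportion used for power (above 30%) at 3 months.

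**Text that points to 6 weeks.** The footnote to the visit schedule (B.9.1.5) reads "Primary outcome assessment will occur at any point upto 6 weeks post ED visit dependent on routine care visit". B.9.1.4 describes the 3-month contact as a "second follow-up survey and end of study (EOS) via telephone to assess secondary outcomes".

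**Text that does not settle it.** Table 2 marks the primary outcome at week 6 and at month 3. The visit schedule marks outcome ascertainment at both. B.10.2 plans logistic models at both.

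**The debrief.** B.9.1.6 says that participants "following primary outcome ascertainment will be debriefed regarding the study and its purpose/goals", without naming a time. B.9.1.3 says "The debrief will be conducted after the 1st survey", although the sentence two before it ties the debrief to completion of the follow-up surveys, in the plural. The visit schedule marks debriefing in the 6 WK column only. Participants are then told that "they participated in a study evaluating methods to improve continuity of gout care".

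**The concern.** A primary outcome needs one time point, fixed before data are seen. Here two analysts could each cite the plan and report different primary results, one at 6 weeks and one at 3 months.

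The debrief depends on which is meant. Its placement at week 6 agrees with B.9.1.6 only if 6 weeks is primary. If 3 months is primary, the topic of the study is disclosed while the primary outcome is still accruing. B.8.1 makes that outcome self-reported and already concedes recall and social desirability bias. A reminder that the study is about continuity of gout care could prompt a visit or colour the report of one. The plan evidently meant to avoid this, since B.9.1.6 holds the debrief back until ascertainment is done.

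**Working it through.** **1. Passages side by side**

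| Section | If 3 months is primary | If 6 weeks is primary |
|---|---|---|
| B.8.1, Table 2 footnote, B.10.2 test, B.11 | consistent | must be restated |
| B.9.1.5 footnote, B.9.1.4 | must be corrected | consistent |
| B.9.1.3 (primary-outcome questions at week 6) | consistent with Table 2 | consistent |
| B.9.1.3 and schedule (debrief at week 6) against B.9.1.6 | conflict | consistent |

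No column is free of conflict, so the passages cannot be reconciled by interpretation alone.

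**2. Time left after the debrief, 3-month reading**

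Take 3 months as about 13 weeks. Then 13 − 6 = 7 weeks remain, and 7/13 = 54% of calendar time. This is not a share of visits. B.5.3 cites an average wait of 9 to 10 weeks for a new rheumatology patient. Such a visit would fall 9 − 6 = 3 to 10 − 6 = 4 weeks after the debrief. Some qualifying visits would therefore follow disclosure. The documents do not give the proportion.

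**3. The stated power, reproduced at 3 months**

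Inputs from B.11: 200 analysed, 2:1 allocation (67 control, 133 intervention), relative risk 1.68, control proportion 30%, two-sided 0.05. With p1 the control and p2 = 1.68 × p1 the intervention proportion, and the pooled variance under the null:

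power = Φ[(|p2 − p1| − 1.96 × SE0) / SE1], where SE0 = √[p̄(1 − p̄)(1/67 + 1/133)] and SE1 = √[p1(1 − p1)/67 + p2(1 − p2)/133].

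- p2 = 1.68 × 0.30 = 0.504
- p̄ = (67 × 0.30 + 133 × 0.504)/200 = 0.4357
- SE0 = 0.0743 and SE1 = 0.0708
- (0.204 − 1.96 × 0.0743)/0.0708 = 0.825, so power is 79.5%

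This agrees with the stated 80%. The sample size statement is sound as a 3-month calculation.

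**4. The same formula on the 6-week reading**

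The documents give no 6-week control proportion, so the values below are assumptions. The relative risk and the 67 and 133 are kept, although 200 rests on the 3-month non-response rate.

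| Assumed 6-week control proportion | Power for relative risk 1.68 |
|---|---|
| 15% | 37% |
| 20% | 52% |
| 25% | 66% |
| 30% | 80% |
| 35% | 90% |
| 40% | 96% |

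**5. Participants who would need a written debrief if it moves**

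B.11 expects about 280 randomised and 30% non-response at 3 months: 280 × 0.30 = 84.

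**The case against.** The strongest reply is that the plan really means 3 months and that the contrary text is slight: one footnote, and a B.9.1.4 phrase whose only support is a list of examples. Four definitional or statistical statements stand against it. That is a fair reading, and it is why 3 months is taken below as the likely intent. But it leaves the footnote's 6-week cap unexplained, and it is the reading on which the debrief comes too early.

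Four stronger claims are tempting, and the documents do not support them.

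- *B.9.1.3 shows that 6 weeks is primary*, because there "the survey questions used to collect the primary outcomes will be sent via email or text messaging" to participants not reached by phone. Table 2 collects the outcome at both times, so asking about it at week 6 is expected under a cumulative 3-month outcome. That sentence needs no correction.
- *Most qualifying visits come after the debrief.* The 9 to 10 week wait is for new rheumatology patients, while primary care visits also count. The navigator text calls an appointment sooner than one month unlikely, but a visit in weeks 4 to 6 satisfies that and precedes the debrief.
- *The early debrief biases the result.* The debrief is described as disclosing the topic, not the arm. Consent already outlines the purpose (B.6), controls also receive a gout-related referral (B.5.3), and the week-6 survey is itself a cue. Nor does B.9.1.3 describe a debrief for those who answer by email or text.
- *The stated power fails at 6 weeks.* A cumulative proportion at 6 weeks cannot exceed the one at 3 months, but B.11 gives 30% as a floor, and B.8.1 puts post-ED follow-up for many chronic diseases nearer 50%. The 6-week proportion could be below or above 30%.

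**Conclusion.** The inconsistency is real, lies in the current text, and should be fixed. The weight of the definition, analysis and power statements favours 3 months. On that reading, the debrief in B.9.1.3 and the visit schedule contradicts B.9.1.6. Participants who complete the week-6 telephone survey are told the topic about 7 weeks before the window of a self-reported primary outcome closes.

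This is an avoidable threat to the outcome, not a demonstrated bias; neither its size nor its direction can be worked out from the documents. The 7 weeks assume a 13-week window and a survey held on schedule.

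On the 6-week reading the debrief is in the right place, but 80% power is not established. It would run from 37% to 96% over assumed control proportions of 15% to 40%, with the analysed number held at 200.

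**What to change.** State 3 months as the single Aim 2 primary time point.

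- Correct the visit-schedule footnote in B.9.1.5 and the description of the 3-month survey in B.9.1.4.
- Label the 6-week model in B.10.2 as secondary.
- Move the debrief in B.9.1.3 and the visit schedule to after 3-month ascertainment, so that both agree with B.9.1.6, and remove the mismatch in B.9.1.3 between surveys in the plural and the first survey.
- Provide a written debrief for participants not reached at 3 months.

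**Cost.** An IRB amendment and a change of call script, with no extra visits. Participants are debriefed about 7 weeks later. About 84 of 280 would depend on a written debrief, and some may not receive it, because email and text are also contact routes in D.2 that may already have failed. Those who answer at week 6 but not at 3 months would lose the live debrief they now get.

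**If the team intends 6 weeks instead,** leave the debrief where it is. Restate B.8.1, the Table 2 footnote and the B.10.2 test at 6 weeks, and redo B.11 with a 6-week control proportion and a 6-week non-response rate.

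### The V3 footnote lets the date of the 6-week assessment follow the routine care visit, which can itself be the outcome, and conflicts with the fixed 6-week contact in B.9.1.3

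*Combined protocol and SAP*

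**What the plan says.** The visit schedule (B.9.1.5) attaches this footnote to V3, the 6-week column: "Primary outcome assessment will occur at any point upto 6 weeks post ED visit dependent on routine care visit". B.9.1.3 sets V3 by the calendar: "At 6 weeks following ED visit, participants will be contacted by the Coordinating Center (CC". B.9.1.4 likewise places the second survey at 3 months for everyone, but describes it as assessing secondary outcomes.

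B.8.1 defines the Aim 2 primary outcome as "the proportion of patients that have a follow-up visit addressing gout in the 3-month period after the ED visit", with survey self-report as the primary source and record review alongside. B.10.2 analyses "persons receiving at least one outpatient gout follow-up visit at 3 months" and adds that logistic models "will be developed for 6 week outcomes and 3 month outcomes". Table 2 marks the primary outcome at both week 6 and month 3. It also marks flares, ED visits, hospitalizations and EQ-5D at week 6. B.10.3 plans t-tests or linear regression for secondary outcomes and mentions no follow-up time.

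B.9.1.3 places the debrief after the first survey. In the navigated arm, B.9.1.2 has navigators call in the week "prior to their visit to confirm the appointment time". The documents do not define a routine care visit, say how it would trigger the assessment, or say which record counts if week 6 and month 3 disagree.

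**The concern.** Two timing rules govern the same contact. Under B.9.1.3 the V3 date does not depend on what happens to the patient. Under the footnote it does, and the event that moves it is, or overlaps with, the primary outcome. A patient with an early visit could be assessed early, while a patient without one waits until week 6.

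Three things follow if the footnote is applied:

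- **Exposure.** If the whole V3 survey moves with the primary outcome question, early visitors have fewer days in which to report a flare, ED visit or hospitalization, and they answer the EQ-5D sooner after the index flare. An arm with more early visits would then show fewer 6-week events with no true effect. The planned methods do not adjust for this.
- **Debrief.** It follows the first survey, so visitors would be told the study's purpose earlier than non-visitors. Everyone is debriefed before month 3 in any case. The footnote adds a dependence of the debrief date on the outcome, ahead of a self-reported 3-month endpoint.
- **Early negative answers.** A routine visit that did not address gout could trigger an early no. A later gout visit would then be missed unless the 3-month survey overrides that answer, and B.9.1.4 does not say that it does.

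**Working it through.** **1. The plan's own figure.** B.11 states 80% power for a relative risk of 1.68 with 200 patients, 2:1 allocation, a 30% control rate and two-sided alpha 0.05.

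- Intervention rate: 0.30 × 1.68 = 0.504. Pooled rate: (0.30 + 2 × 0.504)/3 = 0.436. Arm sizes: 66.7 and 133.3.
- Null standard error: √(0.436 × 0.564 × 0.0225) = 0.0744.
- Alternative standard error: √(0.30 × 0.70 × 0.015 + 0.504 × 0.496 × 0.0075) = 0.0709.
- z = (0.204 − 1.96 × 0.0744)/0.0709 = 0.82, so power is 79.4%.

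The stated 80% reproduces. It concerns the 3-month outcome, and fixed assessment dates leave it unchanged.

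**2. Length of the 6-week window if V3 follows the visit.** The 3-month visit rates (30% and 50.4%) come from B.11. The share *s* of those visits that falls by week 6 is not in the documents and is varied here. The calculation assumes that V3 takes place on the day of the visit and at week 6 otherwise, and that the arms already differ before week 6 in the ratio 1.68.

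Mean window = 6 − p·s·(6 − m), where p is the 3-month visit rate and m is the mean week of the early visits.

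Early visits spread evenly over weeks 0 to 6 (m = 3):

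| s | Control, weeks | Intervention, weeks | Intervention shorter by |
|---|---|---|---|
| 25% | 6 − 3 × 0.075 = 5.78 | 6 − 3 × 0.126 = 5.62 | 2.6% |
| 50% | 6 − 3 × 0.150 = 5.55 | 6 − 3 × 0.252 = 5.24 | 5.5% |
| 75% | 6 − 3 × 0.225 = 5.33 | 6 − 3 × 0.378 = 4.87 | 8.6% |
| 100% | 6 − 3 × 0.300 = 5.10 | 6 − 3 × 0.504 = 4.49 | 12.0% |

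A constant visit hazard over 13 weeks gives 5.53 against 5.13 weeks, 7.3% shorter.

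B.5.2 and B.9.1.2 call an appointment within a month unlikely, and B.5.3 cites an average wait of 9 to 10 weeks for a new rheumatology patient. Placing early visits in weeks 4 to 6 (m = 5) fits those statements better:

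- s = 100%: 6 − 0.300 = 5.70 against 6 − 0.504 = 5.50, 3.6% shorter.
- s = 50%: 6 − 0.150 = 5.85 against 6 − 0.252 = 5.75, 1.7% shorter.
- s = 25%: 6 − 0.075 = 5.93 against 6 − 0.126 = 5.87, 0.9% shorter.

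If events occur evenly in time at the same rate in both arms, the spurious deficit in 6-week event counts equals the shortening.

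**3. The binary primary outcome.** When a gout visit triggers the call, the patient is already a positive. A patient with no visit is still followed to week 6. The shortening therefore removes no primary event. The exception is a trigger by a visit that did not address gout.

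**4. Capture that depends on the outcome.** If visitors respond with probability r1 and non-visitors with r0 in both arms, each arm's odds are multiplied by r1/r0 and the ratio cancels. The odds ratio stays at (0.504 × 0.70)/(0.496 × 0.30) = 2.37. Bias in the planned logistic model needs capture to differ by arm as well as by outcome.

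**The case against.** The strongest reply is that the footnote may only mean that the care visit can occur at any time up to week 6, which makes this a drafting slip. It also names only the primary outcome assessment, so extending it to flares and EQ-5D is an inference. Both points stand as far as they go: the exposure effect holds only if the other V3 items move too. But the wording is about when assessment occurs, V3 is a single contact, and nothing separates the primary question from the rest of the survey.

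Other parts of the plan limit the damage. The footnote does not move the 3-month contact. Section C documents adverse events from consent until 7 days after the last participation, so an early V3 does not cut off their collection. ED visits and hospitalizations after an early V3 can still be picked up at month 3. B.10.3 calls the secondary endpoints hypothesis-generating. All of this stands.

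A reader might go further and infer that whether a patient is reached depends on the outcome, and more so in the navigated arm, so that the test is anti-conservative. A hypothetical for the 6-week visit rate shows what that would take. Suppose a true rate of 30% in both arms, visitors captured at 90% in the intervention arm only, and everyone else at 60%. The observed rates are then 0.27/(0.27 + 0.42) = 39% against 30%, with about 21% rejections at about 129 and 56 responders. The documents do not support those inputs. The footnote governs timing. The Coordinating Center makes the survey contact, and no section says that navigators pass appointment dates to it. D.2 gives both arms the same contact attempts and fallbacks. B.11 does expect slightly unequal non-response between arms, but states no direction and no link to visits.

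**Conclusion.** The conflict between the footnote and B.9.1.3 is in the current text and needs no assumption. If the footnote is followed, the V3 date depends on an event that is, or overlaps with, the primary outcome.

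The numerical effect is small to moderate. The intervention arm's mean 6-week window is roughly 2 to 12% shorter when at least a quarter of the 3-month visits fall by week 6 and are evenly spread, or when at least half do and they fall in weeks 4 to 6. The latter, which agrees better with the plan's own remarks on waiting times, gives about 2 to 4%; a quarter of visits in weeks 4 to 6 gives under 1%. All these figures assume that V3 happens on the visit day, that its other items move with it, and that the arms differ before week 6. They bear on hypothesis-generating 6-week measures.

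The 3-month primary analysis is touched only indirectly, through the uneven debrief and the possible early negative answer. An inflated false-positive rate for the primary test is not shown. This is a cheap improvement worth making.

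**What to change.** Replace the whole footnote. Deleting only the clause about the routine care visit would leave an assessment at any time up to week 6, which still disagrees with B.9.1.3 and with a 3-month endpoint. The new text should say:

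- V3 opens at 6 weeks and V4 at 3 months from the ED visit, with the same contact windows in both arms, whether or not a visit has occurred.
- Each survey records the dates of outpatient visits and whether they addressed gout. The V4 survey covers the whole period since the ED visit, and the 3-month primary outcome is classified by visit date from that record, so that an earlier negative answer can be superseded.

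Bring B.9.1.3, B.9.1.4 and Table 2 into line, including a statement in B.9.1.4 that V4 ascertains the primary outcome. In B.10.3, analyse counts of flares, ED visits and hospitalizations with a count regression that uses the log of actual follow-up days as the offset; a t-test cannot carry this.

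The cost is one footnote, matching edits in a few sections and a date field on the survey. Patients with early visits will have slightly longer recall. The sample size and the 3-month power do not change.
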